#### **11.1.13. Pharmacokinetics**

All plasma samples for determination of BCX7353 concentrations will be analyzed using a validated liquid chromatography-mass spectroscopy assay. Instructions for collection, processing, storage, and shipment of PK samples will be provided to the clinical site in the laboratory manual. Samples may also be analyzed on an exploratory basis for possible BCX7353-metabolites.

On Day 14 serial blood samples will be drawn for PK analysis predose and at the following time points: 1, 2, 3, 4, 5, 6, 8, and 24 hours postdose. For the 24 hour postdose samples, subjects will return to the clinic and have the blood sample drawn prior to dosing on Day 15. On Day 29, a trough PK blood sample will be drawn.

However, if the subject is unable to provide serial PK samples on Day 14, only the predose sample (i.e., trough PK sample) will be obtained on Day 14 and steady state serial PK samples will be obtained on Day 28, with a 24-hour PK sample drawn at the scheduled visit on Day 29.

Within 6 hours postdose, an acceptable window around each PK draw is  $\pm 10$  minutes. After 6 hours, an acceptable window is  $\pm 20$  minutes. Predose samples should be drawn within 5 minutes of the next scheduled dosing time.

Plasma BCX7353 PK parameters will be calculated as applicable, including the following: maximum concentration ( $C_{max}$ ), time to  $C_{max}$  ( $T_{max}$ ), area under the concentration versus time curve (AUC), and 24 hour half-life ( $t_{1/2}$ ) in plasma.

Actual date and time of PK sample collection will be recorded in the eCRF. In addition, the site should verify that the time of last dose taken at home prior to the visit is documented in the diary.

The lab performing bioanalytical analysis will be provided the randomization scheme. Two samples will ordinarily be analyzed for subjects randomized to placebo: the 4 hour postdose sample on Day 14 and the trough at Day 29.

#### **11.1.14. Pharmacodynamics**

On Day 1 and Day 14 a plasma sample for plasma kallikrein analysis will be drawn prior to dosing and, on Day 14, at 1, 2, 3, 4, 5, 6, 8, and 24 hours postdose. The Sponsor may waive the participation in any or all serial PD sampling on a case by case basis. A sample for plasma kallikrein analysis will also be drawn on Day 29.

A plasma sample for possible exploratory analysis used to elucidate PD properties of BCX7353 will be drawn on Day 1, Day 14, and Day 29.

Instructions for collection, processing, storage and shipment of samples will be provided in a separate document.

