### 13.2.7. Pharmacodynamic Analysis

On-treatment plasma kallikrein inhibition data will be expressed as percent inhibition compared to subject baseline activity. Ex vivo plasma kallikrein activity will be listed by subject, treatment, day, and time and summarized separately by treatment, day, and time. Descriptive statistics will be reported. Mean and individual plasma kallikrein inhibition versus time profiles will be plotted by treatment group.

C1 INH functional levels and absolute change from baseline will be summarized.

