- n Subjects will be randomized by the Sponsor on or after the screening visit and is contingent upon review of screening visit data entered into the eCRF subsequent questions the Sponsor may have. Randomization will trigger shipment of a kit of study drug for the first 14 days and an automatic resupply to arrive on-site at approximately study Day 10 after entry into the eCRF system that the subject has had a Day 1 visit. More details on randomization and kit shipment will be provided to the site.
- o The Investigator (or designee) will provide a diary for collection of HAE attacks (screening through follow-up) and study drug dosing (Days 1-28) at screening, Day 1, Day 14 and Day 29. Diaries will be collected on Day 1 (screening diary), Day 14, Day 29 and follow-up. At each visit and phone call, the Investigator (or designee) will review proper recording of attacks and dosing (as applicable) in the diary.
- p At any time the diary is in a subject's possession, they will enter HAE attacks and relevant details and dosing information (as applicable) at least once per day.
- q On Day 14, a blood sample for plasma PK and plasma kallikrein analysis will be drawn prior to dosing ( $< 5$  min) and at 1, 2, 3, 4, 5, 6, 8, and 24 hours postdose (i.e., on Day 15); Day 29 will be trough samples. If the subject is unable to provide serial PK samples on Day 14, steady state PK samples may be obtained on Day 28, with a 24-hour PK sample drawn at the scheduled visit on Day 29. In this case, trough PK samples will be drawn on Day 14. If the subject has a Day 29 visit for the 24-hour PK sampling, concomitant medications and AEs should also be assessed at the visit. Within 6 hours postdose, an acceptable window around each PK draw is  $\pm 10$  minutes. After 6 hours, an acceptable window is  $\pm 20$  minutes. Plasma PK and plasma kallikrein samples will be collected prior to in clinic dosing on Day 1 and Day 14. The Day 29 samples will be collected approximately 24 hours post-last dose.
- r Cleaved HK and an additional sample for possible exploratory analysis used to elucidate PD properties of BCX7353 will be drawn.
- s Subjects will take their study drug in the clinic on Day 1, Day 14 and Day 15 (Day 28 if subjects must complete serial PK on the last dose). Subjects will take all other doses at home as instructed. The last day of study drug dosing is Day 28.

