## 10.3. Baseline Definition

Baseline is the last available assessment prior to the time of first dose unless otherwise specified.

The study qualifying attack rate will be used as baseline for the attack rate endpoint and is defined as follows:

Subject Reported Qualifying attack rate:

$$\frac{\text{Total Number of Qualifying attacks reported} * 7}{\text{Duration of Qualifying reporting period in days}}$$

Duration of qualifying attack reporting period is calculated as number of days as the last date of the period – the first date of the reporting period +1.

Adjusted Qualifying attack rate:

$$\frac{\text{Total Number of Adjusted Qualifying attacks reported} * 7}{\text{Duration of Qualifying reporting period in days}}$$

Duration of qualifying attack reporting period is calculated as number of days as the last date of the period – the first date of the reporting period +1

For subject reported historical attacks on consecutive days, these attacks will be counted as a single attack in the calculation of the adjusted qualifying attack.

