## 14. PHARMACODYNAMIC ANALYSES

### 14.1. Kallikrein Inhibition, Cleaved HK Fragments, and C1 INH

On-treatment plasma kallikrein inhibition data (assessed with and without stimulation by ellagic acid) will be expressed as percent inhibition compared to subject baseline activity. Ex vivo plasma kallikrein activity will be listed by subject, treatment, day, and time and summarized separately by treatment, day, and time. Descriptive statistics will be reported. Mean and individual plasma kallikrein inhibition versus time profiles will be plotted by treatment group. Plasma kallikrein inhibition data from Day 14 or Day 28 will be combined by treatment group for analysis. The difference between each active treatment group vs placebo and between active doses in plasma kallikrein inhibition will be analyzed using a repeated measures analysis of variance with time, treatment and time by treatment as fixed effects. Subject will be fitted as a random effect in the model. The point estimates and corresponding 95% confidence interval (CI) for treatment differences will be calculated at each time point.

Cleaved HK fragments and C1 INH functional levels and absolute change from baseline will be summarized by treatment group. The HK end of treatment /Baseline ratio will also be listed and summarized by treatment group. The difference between each active treatment group and placebo and the pairwise difference between active doses in C1inh Change from baseline, cleaved HK change from baseline and HK end of treatment /Baseline ratio will be analyzed using ANOVA with treatment as fixed effects. Baseline value will be included as a covariate. The point estimates and corresponding 95% confidence interval (CI) for treatment differences will be calculated for each comparison.

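### Percent kallikrein inhibition rests on one Day 1 pre-dose sample per subject, and its SAP model has no baseline covariate, so contrasts involving placebo or low doses are likely less precise than the collected data allow

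*Protocol*

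**What the plan says.** Protocol 11.1.14 sets the kallikrein sampling: "On Day 1 and Day 14 a plasma sample for plasma kallikrein analysis will be drawn prior to dosing", then serial draws on Day 14 and one on Day 29. The SAP schedule footnote agrees: "Plasma PK and plasma kallikrein samples will be collected prior to in clinic dosing on Day 1 and Day 14". Neither schedule table has a kallikrein sample at screening.

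SAP 10.3 defines baseline: "Baseline is the last available assessment prior to the time of first dose unless otherwise specified". For kallikrein that is the single Day 1 draw. SAP 10.5 averages repeat measurements, but only one pre-dose draw is scheduled.

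Under SAP 14.1 the on-treatment data "will be expressed as percent inhibition compared to subject baseline activity"; Protocol 13.2.7 says the same. The model is a "repeated measures analysis of variance with time, treatment and time by treatment as fixed effects", and "Subject will be fitted as a random effect in the model". Differences from placebo and between active doses are estimated with 95% intervals at each time point.

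The next paragraph of SAP 14.1 covers change in C1 INH, change in cleaved HK and the HK end-of-treatment/baseline ratio. There, "Baseline value will be included as a covariate". SAP 9.3 lists covariates for efficacy only, so it does not bring baseline into the kallikrein model.

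**The concern.** Dividing by baseline is not the same as adjusting for it. On the log scale, division fixes the coefficient of baseline at 1. If baseline is measured with error, the best coefficient is smaller. A baseline that is low by chance then gives falsely low inhibition at every later time point for that subject.

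Serial draws do not average this error out, because they share the denominator. The random subject effect describes the shared error but cannot remove it from the contrasts, because treatment varies between subjects.

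What is at stake is precision, mainly for the 62.5 mg arm, planned at 6 subjects in the three parts that the SAP covers. The SAP adjusts one ratio to baseline (HK) for its baseline and not the other (kallikrein), and gives no reason.

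**Working it through.** **No plan figure to reproduce.** The documents give no SD, power or precision target for kallikrein inhibition. The sample-size tables concern attack rate and attack-free proportion.

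**Inputs from the documents**
- Planned arms: placebo 18 + 2 + 2 = 22; 62.5 mg 6; 125 mg 6 + 6 = 12; 250 mg 6 + 6 = 12; 350 mg 18.
- Mean inhibition at the end of the dosing interval: 42% at 125 mg and 76% at 250 mg (Protocol 5.4.1.3).

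**Assumed, not in the documents**
- Within-subject CV 10-25%; between-subject CV of baseline 15-25%.
- True inhibition, mean (SD): 0 on placebo, 20 (10)% at 62.5 mg, 42 (15)% at 125 mg, 76 (10)% at 250 mg, 80 (8)% at 350 mg.

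**Step 1. Weight of the baseline error.** Let I be true inhibition, e0 the log error in the baseline sample and et the log error in the later sample. Then

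y = 100 × [1 − (1 − I) × exp(et − e0)],

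so the error in y is about −100 × (1 − I) × (et − e0). The weight on e0 is residual activity, 1 − I:
- placebo: 1 − 0 = 1.00
- 62.5 mg: 1 − 0.20 = 0.80 (assumed)
- 125 mg: 1 − 0.42 = 0.58
- 250 mg: 1 − 0.76 = 0.24

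The weight also varies over the interval. Protocol 5.3.3.2 gives about 60% maximum inhibition at 125 mg, so the weight there is about 0.40.

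**Step 2. What a covariate can remove.** Let ρ be baseline reliability: between-subject log variance over total log variance, where log variance = ln(1 + CV²). Adjusting for observed log baseline leaves a fraction ρ of the e0 variance. In the placebo arm at one time point, the variance ratio (adjusted/unadjusted) is (1 + ρ)/2.
- Within 10%, between 25%: ρ = 0.0606/(0.0606 + 0.0100) = 0.86; ratio 0.93.
- Within 25%, between 15%: ρ = 0.0223/(0.0223 + 0.0606) = 0.27; ratio 0.63.
- ρ = 0.95: ratio 0.975, or about 1% in SE.

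The contrast of 62.5 mg with placebo gains less than placebo alone, because baseline does not explain the spread of true inhibition among the 6 treated subjects.

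**Step 3. Simulation, 62.5 mg vs placebo, one time point.** SAP model against the same model with a common slope on log baseline, 4000 trials per setting:

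| Within CV | Between CV | Variance ratio | Interval-width ratio (square root) |
|---|---|---|---|
| 10% | 15% | 0.92 | 0.96 |
| 10% | 25% | 0.98 | 0.99 |
| 15% | 15% | 0.83 | 0.91 |
| 15% | 25% | 0.92 | 0.96 |
| 25% | 15% | 0.73 | 0.85 |
| 25% | 25% | 0.81 | 0.90 |

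The variance falls by 2-27% and the width by 1-15%. For 125 vs 62.5 mg the variance ratio runs from 0.75 to 0.99. Estimated treatment differences moved by at most about 0.3 percentage points.

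**Step 4. Second simulation on a different footing.** This used a sigmoid curve through the 42% and 76% points, between-subject trough variability from Protocol Table 2, within-subject CV 10-30%, and a common slope on untransformed baseline. The SE ratio for 62.5 mg vs placebo at one time point was 0.87-0.89 at ρ = 0.3, 0.91 at 0.5, 0.96 at 0.7, 0.98-0.99 at 0.9 and about 1.00 at 0.95.

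**Step 5. The form of the covariate matters.** The weights in Step 1 differ by arm, so one slope cannot suit all arms.
- *Common slope:* variance of 350 vs 250 mg rises by about 4-23% in the Step 3 settings (square roots 1.02 and 1.11, so 2-11% wider intervals).
- *Separate free slope per arm:* variance of 62.5 mg vs placebo rises by 1-19% in four of the six settings, because one slope is estimated from 6 subjects.
- *One slope scaled to residual activity:* the 350 vs 250 mg penalty disappears (SE ratio 0.84-1.00 in the second simulation, computed on each subject's mean over the serial samples), and the low-dose gains are kept.

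**The case against.** **The size depends on assay properties nobody has stated.** This stands. Within-subject error, baseline reliability and inhibition at 62.5 mg are all assumed. One draw need not mean one determination: sample processing is left to a separate document, and replicate number is not given. If baseline is very reliable, nothing is gained.

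**Nothing in the planned analysis is invalid.** This stands too. The random subject effect carries the shared error, and the treatment difference barely moves. A reader might infer that the contrasts are biased; the calculations do not support that.

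**The model does not choose the dose.** A reader might infer that imprecision here undermines dose selection, since Protocol 5.4.1.3 cites 42%, 62% and 76% inhibition. The documents do not support that. The 62% at 175 mg is a prediction. The concentration-inhibition relation is described by a sigmoidal Emax model (Protocol 5.3.3.2), which is what the 62.5 mg data are expected to refine. SAP 14.2 handles exposure-response separately.

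**Gains from averaging the serial draws do not count.** A reader might expect a larger gain there, but the SAP estimates differences at each time point, and the Sponsor may waive any or all serial PD sampling.

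**A simple covariate harms one planned contrast.** This is correct for 350 vs 250 mg with an unscaled common slope, and it shapes the fix.

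What survives is that a baseline already collected, and already used in this way for two other markers in the same section, is left out without explanation.

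**Conclusion.** The point holds as an optional precision improvement to a secondary PD analysis, in a study with no formal hypotheses. The textual facts are clear: one Day 1 denominator, no baseline term for kallikrein, and a baseline term for C1 INH and cleaved HK. The direction follows from the algebra whenever baseline is measured with error.

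The likely size for 62.5 mg vs placebo, per time point, is 2-27% in variance or 1-15% in interval width under the assumed CVs. It is near zero at baseline reliability of 0.95 or above. Contrasts of higher doses with placebo also gain, because placebo carries the full weight; among active-dose contrasts, those involving low doses gain most. There is no material bias, and no stated sample size or power changes.

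**What to change.** In SAP 14.1, add log Day 1 pre-dose kallikrein activity and its interaction with time to the repeated-measures model for percent inhibition, for both assays (Tables 14.2.6.3 and 14.2.6.4). Preferably scale the slope to each arm's residual activity. Do not fit free treatment-specific slopes with only 6 subjects at 62.5 mg.

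As a sensitivity analysis, model log on-treatment activity with log baseline as covariate and back-transform to percent inhibition. For C1 INH and cleaved HK, SAP 14.1 plans treatment differences with intervals but does not mention LS means at the mean baseline. If adjusted means are wanted for kallikrein, specify the baseline value at which they are evaluated.

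The cost is a few degrees of freedom and a somewhat longer model specification, fixed before database lock. No new data are needed. If an unscaled common slope is used for simplicity, state that it is expected to widen the 350 vs 250 mg interval.

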### **11.1.15. HLA Typing**

All subjects will have a blood sample drawn at Baseline/Day 1 (or any other time point on study if not obtained at Baseline) for HLA-typing. Samples will be sent to a central laboratory for analysis. The results will not be communicated back to the investigator or subjects because the results are not intended for diagnostic or prognostic purposes and will be used in a research related fashion only.

### **11.1.16. Possible Exploratory Pharmacogenomics Testing**

All subjects who are willing to participate and sign a separate informed consent will have a blood sample drawn at Baseline / Day 1 (or any other time point on study if not obtained at Baseline) for possible exploratory pharmacogenomics testing. Testing may be undertaken in one or more locus/loci if desired by the Sponsor to examine whether allelic variations account for efficacy or safety findings. Samples will be sent to a central laboratory for analysis and results will not be returned to sites.

## **11.2. Subject-Completed Assessments**

### **11.2.1. Quality of Life Questionnaires**

To assess quality of life, the AE-QoL and DASS questionnaires will be administered once at Baseline, Day 14 (DASS only) and at Day 29.

For all subject-completed forms, clinic staff should ensure the subject reads the instructions and completes the questionnaires in full prior to filing in the source documentation.

### **11.2.2. HAE Attack and Dosing Diaries**

The Sponsor will supply paper diaries to all sites. Sites will dispense diaries to subjects at screening, Day 1, Day 14 and Day 29. Diaries will be collected on Day 1, Day 14, Day 29 and at follow-up.

At the Screening visit, subjects will be instructed how to complete the diary for an attack. While a subject has a diary in their possession, the subject will fill out the HAE attack diary daily, recalling whether symptoms of an HAE attack were experienced in the last 24 hours. Subjects must fill out the diary daily, regardless of the presence of HAE symptoms. If the subject does report an attack in their diary, additional details about the attack will be required, including location of the symptoms of the attack, severity, and treatment(s) administered and times of administration. During the treatment period, subjects will also record the time of day study drug was taken, and the number of capsules of study drug taken at each dose in the diary on a daily basis. Study drug doses administered in the clinic will be entered into the diary on site.

The Investigator (or designee) will proactively assess completion of the diary, during visits on Days 1, 7, 14, 21 and 29. While study staff are not permitted to make any entries into the diary, subjects may be asked to rectify incomplete diary entries made since the last visit/phone call based on outstanding questions a subject may have or incorrect assumptions/interpretation of diary questions.

Further training on completing the diary should be provided at each clinic visit or where required, during a telephone call.

## **12. ASSESSMENT OF SAFETY**

### **12.1. Adverse Events**

AEs will be assessed and recorded from the time of signing of the informed consent through the appropriate follow-up period. Full details on recording and reporting AEs are provided in Section [12.1.2](#).

#### **12.1.1. Definitions**

##### **12.1.1.1. Adverse Event**

An AE is any untoward medical occurrence in a clinical study subject. No causal relationship with the study drug/ IMP or with the clinical study itself is implied. An AE may be an unfavorable and unintended sign, symptom, syndrome, or illness that develops or worsens during the clinical study. Clinically relevant abnormal results of diagnostic procedures including abnormal laboratory findings (e.g., requiring unscheduled diagnostic procedures or treatment measures, or resulting in withdrawal from the study) are considered to be AEs.

This includes the following:

- AEs not previously observed in the subject that emerge during the protocol-specified AE reporting period (see Section [12.1](#)), including medical triggers resulting in an HAE attack. Emotional stress will not be considered an AE unless it results in a medical diagnosis or requires medical treatment.
- Findings from protocol-mandated interventions. This can include laboratory assessments performed in the course of the clinical trial. AEs should only be reported if the abnormalities are changes from baseline and are clinically significant as described above.
- Pre-existing medical conditions (other than the condition being studied) judged by the investigator to have worsened in severity or frequency or changed in character during the protocol-specified AE reporting period

An adverse reaction is defined in Article 2(n) of Directive 2001/20/EC as follows: all untoward and unintended responses to a study drug/IMP related to any dose administered. The definition covers also medication errors and uses outside what is foreseen in the protocol, including misuse and abuse of the product. The definition implies a reasonable possibility of a causal relationship between the event and the study drug/IMP. This means that there are facts (evidence) or arguments to suggest a causal relationship.

For the purposes of this protocol, HAE attacks and their associated symptoms will not be defined as AEs, unless they meet the criteria for a SAE. HAE attacks and associated symptoms will be recorded in the subject's diary. The events that may trigger a HAE attack such as an infection or trauma are considered AEs and should be reported as such.

Surgical procedures should not be reported as AEs. The condition for which the surgery is required should be reported as the AE, if it occurs or is detected during the study period. Planned surgical measures permitted by the clinical study protocol and the conditions(s) leading to these

measures are not AEs, if the condition(s) was (were) known before the start of study treatment. In the latter case the condition should be reported as medical history.

Adverse events are designated as “nonserious” or “serious.”

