#### **5.3.3.1. Interim Safety Results**

Overall, once daily dosing of BCX7353 up to 350 mg for 28 days was well tolerated. There were no SAEs reported in Parts 1 or 2 of the study, no Grade 4 TEAEs, and no TEAEs leading to death. The majority of TEAEs were Grade 1 in severity. Three subjects experienced 7 Grade 3 TEAEs, all in the 350-mg dose arm: constipation, abdominal pain, nausea, vomiting, alanine aminotransferase (ALT) elevation, gastrointestinal infection and migraine. Three subjects discontinued study drug due to an AE, all in the 350-mg dose arm: Grade 3 abdominal pain and vomiting, Grade 1 liver disorder, and Grade 3 ALT elevation.

Gastrointestinal-related AEs (primarily mild in severity) were reported more frequently in the 350-mg arm suggesting a dose response. Some GI events, namely nausea and abdominal pain, are also hallmarks of abdominal HAE attacks which were reported more commonly in the 350-mg dose arm (see Section 5.3.3.3 below). It is possible that subjects may have mis-attributed GI TEAEs as abdominal attacks. The incidence of GI events as well as abdominal attacks decreased in the 2 lower dose cohorts compared to the 350-mg dose cohort.

In addition, liver transaminase elevations were noted primarily in the 350-mg dose arm, but may have been confounded by both baseline elevated ALT and AST as well as a much higher rate of past and/or recent androgen use, neither of which were controlled for in the study. No drug rashes were reported in HAE patients as of the interim cutoff. No QTcF increase from baseline or absolute QTcF interval was considered clinically significant, and no TEAEs of arrhythmia were reported.

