**Figure 2: Proportion of Simulated Clinical Trial Subjects Anticipated to Meet or Exceed Target Trough Concentrations**

#### 5.4.1.3. Rationale for Proposed Doses: Part 4

The results of Part 3 will provide robust safety and efficacy data at BCX7353 doses of 125 and 250 mg QD. Both dose levels have been well-tolerated to date during a 28-day dosing regimen. Current safety data suggest that gastrointestinal AEs and liver enzyme abnormalities are dose-related, with the 125-mg dose level currently not associated with either finding and the 350-mg dose level most associated with these findings.

At all dose levels assessed in Parts 1 and 2, HAE attack rates were significantly reduced relative to placebo, with the greatest overall reduction observed at 125 mg QD, corresponding to ~4-fold  $EC_{50}$  on plasma kallikrein and a mean of 42% kallikrein inhibition at the end of a dosing interval. A closer evaluation of the attacks reported by 18 subjects receiving 350mg BCX7353 revealed that BCX7353 had a high degree of efficacy on peripheral attacks, with no effect on abdominal attacks, potentially due to mis-attribution of abdominal TEAEs as attacks. A 250 mg QD dose

did provide proportionally less exposure than a 350 mg dose, however kallikrein inhibition was generally indistinguishable over a dosing interval.

Therefore, the optimal BCX7353 dose is predicted to be one in which GI TEAEs are reduced but where effective plasma concentrations and kallikrein inhibition are maintained to prevent true HAE attacks from occurring. Based on available data this is likely to be in the 125 to 250 mg QD dose range. Following completion of enrollment in Part 3, Part 4 may be initiated in order to fully define the dose-response relationship with a dose intermediate to 125 and 250 mg. The decision to enroll Part 4, including the doses selected for Part 4, will be based on the PK, safety and efficacy results through Part 3 of the study.

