## 7.2. Endpoints

### 7.2.1. Primary Efficacy Endpoint

The primary efficacy endpoint is the number of confirmed HAE attacks during the treatment period in the Full Analysis Set (FAS) population. The number of HAE attacks will be analyzed by treatment group using appropriate descriptive statistics as follows: weekly attack rate, counts

of attacks, proportion of subjects with no attacks, and number of attack-free days. The relative change in attack rate from placebo will also be calculated for each active arm. The FAS includes all randomized subjects who receive at least 1 dose of study drug and have post baseline HAE attack data.

To ensure that consistent, objective assessments are used in accepting subject-reported attack data, a panel of expert physicians in the treatment of HAE patients will adjudicate all subject-reported attacks prior to their inclusion in primary efficacy analyses. The adjudication will be based upon all data provided by the subjects in their study diaries that document reported HAE attacks. A separate charter will describe membership, roles, and processes to be followed by the adjudication panel.

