#### **10.8. Derived Attack Endpoints**

Subject-reported attacks will be adjudicated by the independent Clinical Endpoint Adjudication Panel (CEAP). The attacks that have been confirmed by the adjudication committee will be included in efficacy analyses. The details of adjudication are provided in the CEAP charter.

The attack endpoints described in this section are based on confirmed attacks by the CEAP, however the rate of attacks will also be calculated for all subject reported attacks. Efficacy analyses will be conducted for HAE attacks reported over the entire dosing period (Days 1 to 28

inclusive), during the dosing period in which BCX7353 should be at steady-state conditions (Days 8 to 28, inclusive), and during the entire study period (Day 1 to the last HAE diary in the follow-up period).

The efficacy analyses will be calculated for 3 treatment periods:

- Entire Dosing Period  
Duration (days) = 28 or (Date of last dose –date of first dose+1), whichever is earlier
- Effective Dosing Period  
Duration (days) = 21 or (Date of last dose –date of first dose-6), whichever is earlier
- Entire Study Period  
Duration (days) = Date of last HAE Attack Diary collection during the follow-up –date of first dose

All efficacy analyses will also be run by treatment period and population (FAS or PP).

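### Neither document returns a subject-reported attack rejected by the panel for adverse event assessment, so some non-serious GI drug effects may be missing from tolerability counts by dose

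*Protocol*

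**What the plan says.** **Recording.** Protocol Section 12.1.1.1 opens with a broad definition: "An AE is any untoward medical occurrence in a clinical study subject". It then makes an exception: "HAE attacks and their associated symptoms will not be defined as AEs, unless they meet the criteria for a SAE". Instead, "HAE attacks and associated symptoms will be recorded in the subject's diary". The section does not say whether an attack here means one reported by the subject, judged by the investigator or confirmed by the panel.

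**Adjudication.** Protocol Section 7.2.1 says: "The adjudication will be based upon all data provided by the subjects in their study diaries that document reported HAE attacks". The panel's processes are left to a separate charter. SAP Section 10.8 adds: "The attacks that have been confirmed by the adjudication committee will be included in efficacy analyses". It also plans attack rates for all subject-reported attacks.

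**Overlap of symptoms.** Protocol Section 5.3.3.1 notes that nausea and abdominal pain are typical of abdominal attacks and comments: "It is possible that subjects may have mis-attributed GI TEAEs as abdominal attacks". Sections 5.3.3.3 and 5.4.1.3 repeat this, also in conditional terms.

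**Use in dose choice.** Protocol Section 5.4.1.3 states that "the optimal BCX7353 dose is predicted to be one in which GI TEAEs are reduced" while effective concentrations are kept. Section 9.5.2 lets common mild GI events count as poor tolerability when a change of the Part 1 dose is considered.

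**The concern.** The disease and the drug can produce the same symptoms, and the first classification is made by the subject in a diary. If a drug effect such as abdominal pain is logged as an attack and the panel rejects it, the event leaves the confirmed-attack endpoint. Nothing in either document then prompts anyone to ask whether it was an adverse event.

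Safety and dose-response are both secondary objectives, and GI tolerability by dose feeds the dose decision. If misattribution rises with dose, the GI event counts at different doses would look more alike than they are. Two other steps also rely on AE status. The site asks about food intake when a GI symptom is noted as an AE (Section 9.4), and the data monitoring committee trigger counts AEs and laboratory abnormalities (Section 12.2). Analysts cannot repair the gap later, because AE assessment has to be made at the site.

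**Working it through.** **1. Path of a non-serious GI event logged as an attack**

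| Panel decision | Efficacy outputs | Tolerability outputs |
|---|---|---|
| Confirmed | Primary endpoint; rates by location (SAP 12.1.4); symptom summaries (SAP 10.8.8) | None, by the exception in Protocol 12.1.1.1 |
| Rejected | Subject-reported counts (SAP 12), weekly rate (SAP 10.8.1), ANCOVA (SAP 12.1.3, item 3; Table 14.2.1.15), confirmation summary (Table 14.1.5.6), adjudication listing (16.2.6.2) | None required: no step returns it for AE assessment, and SAP 10.8.8 covers symptoms of confirmed attacks only |

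SAP Section 12.4.2 summarises recorded AEs only. No planned table sets GI events beside abdominal diary events.

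**2. Reproducing the interim figures (Protocol Section 5.3.3.3)**

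Inputs: placebo rate 0.898 per week; reductions of 0.384 (350 mg, n = 18), 0.417 (250 mg, n = 6) and 0.579 (125 mg, n = 7).

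- 0.384/0.898 = 42.8%
- 0.417/0.898 = 46.4%
- 0.579/0.898 = 64.5%

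All three agree with the protocol.

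**3. Implied placebo rates by location** (reduction divided by percentage reduction)

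- Abdominal: 0.053/0.150 = 0.353 and 0.123/0.347 = 0.354. The 350 mg figures give 0.007/0.019 = 0.368, but both inputs are too small and too rounded to be used.
- Peripheral: 0.456/0.840 = 0.543.
- Check: 0.354 + 0.543 = 0.897, against 0.898 stated.

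**4. Scenario for confirmed attacks with abdominal symptoms**

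Assumption, not in the documents: the true effect on abdominal attacks equals the peripheral effect at the same dose.

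Excess = observed abdominal rate − 0.354 × (1 − peripheral reduction). Total = excess × 4 weeks × n.

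| Dose | Observed per week | Expected per week | Excess per week | Total over 28 days |
|---|---|---|---|---|
| 350 mg | 0.354 + 0.007 = 0.361 | 0.354 × 0.28 = 0.099 | 0.262 | 0.262 × 4 × 18 = 18.9 |
| 250 mg | 0.354 − 0.053 = 0.301 | 0.354 × 0.33 = 0.117 | 0.184 | 0.184 × 4 × 6 = 4.4 |
| 125 mg | 0.354 − 0.123 = 0.231 | 0.354 × 0.16 = 0.057 | 0.174 | 0.174 × 4 × 7 = 4.9 |

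If half of the excess were misattributed drug effect, the totals would be about 9, 2 and 2. If the drug truly had no extra effect on abdominal attacks, they would be 0.

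**5. What step 4 does and does not show.** It concerns confirmed attacks, and abdominal here means any attack that included abdominal symptoms, so mixed attacks with peripheral swelling are counted. It gives a scale for the symptom overlap. It says nothing about how many attacks were rejected, and neither document gives that number.

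**The case against.** The strongest reply is that the exception covers attacks, not everything a subject writes in a diary. A rejected event is not a confirmed attack, it fits the general AE definition, and no text forbids recording it. Section 12.1.2 asks the investigator to seek a diagnosis from the presenting signs and symptoms, and AEs and diaries are reviewed at the same visits. GI events were in fact captured under this rule: "Gastrointestinal-related AEs (primarily mild in severity) were reported more frequently in the 350-mg arm suggesting a dose response". The sponsor also read GI events and abdominal attacks together by dose, and the adjudication charter, which was not available for this review, may contain a return step.

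Much of this stands, and it rules out several stronger readings that a reader might infer:

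- *That such events cannot enter the AE record.* The text sets no bar. It lacks a rule, and serious events are exempt from the exception.
- *That rejected events disappear altogether.* They remain in the subject-reported analyses and in the listings.
- *That the sponsor found misattribution to be likely.* The protocol speaks only of a possibility.
- *That about 19 GI events were lost at 350 mg.* That total concerns confirmed attacks under an unverified assumption, and nothing shows that the symptoms were not also recorded as AEs. Returning rejected attacks would recover none of these events.
- *That the loss is shown to be concentrated at higher doses.* The scenario excess is nearly flat between 125 mg (0.174) and 250 mg (0.184), the range that Section 5.4.1.3 names for the likely optimum.

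What the reply does not remove is the missing requirement. Section 11.2.2 describes site review of diary completion, not a judgement between drug effect and attack. The charter is described as covering the panel's membership, roles and processes, whereas AE rules for investigators belong in Section 12. A dose trend in recorded events is compatible with incomplete capture.

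**Conclusion.** The point holds as a gap in the recording rules. Neither document requires AE assessment of a subject-reported attack that the panel rejects, so non-serious drug-related GI symptoms may be missing from the GI event counts by dose. The sponsor uses those counts in dose selection and itself acknowledges possible misattribution.

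The size is unknown. For confirmed attacks with abdominal symptoms at 350 mg, the range is 0 to about 19 events in 18 subjects. The upper end rests on an assumed equal effect on abdominal and peripheral attacks, and the range is no estimate of rejected events. The documents do not show that under-counting has occurred. The conclusion also assumes that the charter contains no return step. The primary efficacy result is not affected. This is an inexpensive improvement that makes GI tolerability by dose more complete.

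**What to change.** 1. In Protocol Section 12.1.1.1, state that a subject-reported attack rejected by the panel is returned, with treatment still blinded, to the investigator for AE assessment.
2. In SAP Section 12.4.2, add one descriptive table by dose. It should show, in separate columns, GI treatment-emergent events and subject-reported attacks with abdominal symptoms and no peripheral swelling, the latter split into confirmed and rejected. The two should not be merged into a composite. At an implied placebo rate of about 0.354 per week (0.354 × 4 = 1.4 per subject over 28 days, mixed attacks included), true attacks could dominate a composite, and efficacy could then pass for better tolerability.

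The second item is needed because the first does not touch confirmed attacks, which is where the interim abdominal signal lies. The primary endpoint and the panel's inputs stay as they are.

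Cost: one sentence in the protocol, a blinded site query for each rejected attack, and one table from diary and adjudication data already collected. Reported GI event counts would probably rise somewhat in all arms, including placebo.
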